# 8.2 Benefits

This research is not designed to benefit study volunteers. Knowledge gained from this research may inform the development of future anti-inflammatory and immunosuppressive medications.

# 9 Research Use of Stored Human Samples, Specimens, or Data

**Intended Use:** Samples and data collected under this protocol may be used to study the body's response to glucocorticoids. Genetic testing will be performed on some of these samples. A separate signed informed consent document will be obtained for any other research not described in this protocol.

**Storage:** Samples will be stored in a secure location with limited access. Samples and data will be coded prior to storage using barcodes assigned by the investigators. The database linking a barcode with a specific individual will be kept in password-protected computers. Only investigators will have access to the samples and data.

**Tracking:** Data acquired under this protocol will be tracked using the Clinical Research Information Management System of the NIAID (CRIMSON). After coding, laboratory specimens will be tracked using the Biological Specimen Inventory (BSI) system, under a NIAID-wide contract for laboratory specimen banking and tracking.

#### Disposition at the completion of the protocol:

• In the future, other investigators (both at NIH and outside) may wish to use these samples and/or data for research purposes. If the planned research falls within the category of "human subjects research" on the part of the NIH researchers, NIH IRB review and approval will be obtained. This includes the NIH researchers sending out coded and linked samples or data and getting results that they can link back to their subjects.

#### Reporting the loss or destruction of samples/specimens/data to the IRB:

- Any loss or unanticipated destruction of samples or data (for example, due to freezer malfunction) that meets the definition of a reportable event will be reported to the NIH IRB according to NIH HRPP Policy 801.
- Subjects may decide at any point not to have their samples stored. In this case, the principal investigator will destroy all known remaining samples and report what was done to both the subject and to the IRB.

# **Handling of specimens/data from subjects who must be removed from the study:** Subjects who are enrolled may need to be removed from the study after the screening visit, if the laboratory and/or ECG results obtained on that visit show an abnormality that meets the study's exclusion criteria. Subjects may also need to be removed from the study if they develop a

condition or side effect that makes them ineligible to continue participation, if the study is cancelled or stopped, or if they fail to comply with the study requirements. In any of these cases, the subject will be notified by the Study Coordinator. Any blood or skin samples collected prior to removal of a subject will be processed in the same way as those obtained from subjects who are not excluded from the study. Data obtained from these samples may be used for the purpose of establishing the level of variation of the baseline measurements under different circumstances, which can be informative. At the time of notification of removal from the study, subjects will be reminded of their right, as detailed in the consent form, to request for their samples to be destroyed. The purpose of this provision is to ensure that research samples of potential use are not unnecessarily destroyed, while effectively respecting the research subjects' right to request destruction of their samples.

# **10** Remuneration Plan for Volunteers

Volunteers will be compensated for their time and inconvenience according to the following schedule:

Screening visit: \$20 for the 1st hour plus \$10 for each additional hour (20+10[3]) = \$50Screening blood draw: \$20 Infusion visit: \$20 for the 1st hour plus \$10 for each additional hour (20+10[6]) = \$80Pre- and post-infusion blood draws: \$20 (x3) = \$60 Pre- and post-infusion punch biopsies of the skin: \$50 (x2) = \$100 Total with biopsy = \$310 Total without biopsy = \$210

In the event that follow-up blood draws need to be scheduled after the infusion visit, as detailed in Section 11.2.1 below, each additional visit will be compensated at \$20.

Volunteers will receive compensation by check, direct deposit, or Automated Clearing House (ACH) payment after their participation in the study is complete.

Travel-related expenses (e.g., transportation, hotel, meals) will not be paid for or reimbursed under this protocol.

# 11 Assessment of Safety

#### **11.1 Definitions**

The NIAID Clinical Safety Office (CSO) is responsible for sponsor safety oversight of this study, and the definitions below comply with CSO requirements.

Adverse Event (AE): An AE is any untoward or unfavorable medical occurrence in a human subject, including any abnormal sign (eg, abnormal physical exam or laboratory finding),

symptom, or disease, temporally associated with the subject's participation in the research, whether or not considered related to the research.

Adverse Reaction (AR): An AE that is caused by an investigational agent (drug or biologic).

**Suspected Adverse Reaction (SAR):** An AE for which there is a reasonable possibility that the investigational agent caused the AE. 'Reasonable possibility' means that there is evidence to suggest a causal relationship between the drug and the AE. An SAR implies a lesser degree of certainty about causality than AR, which implies a high degree of certainty.

Serious Adverse Event (SAE): An SAE is an AE that results in one or more of the following outcomes:

- death
- a life-threatening event (places the subject at immediate risk of death from the event as it occurred)
- an inpatient hospitalization or prolongation of an existing hospitalization
- a persistent or significant incapacity or substantial disruption of the ability to conduct normal life functions
- a congenital anomaly/birth defect
- a medically important event\*

\*Medical and scientific judgment should be exercised in deciding events that may not be immediately life threatening or result in death or hospitalization but may jeopardize the subject or may require intervention to prevent one of the other outcomes listed above.

**Unexpected Adverse Event:** An AE is unexpected if it is not listed in the Investigator's Brochure or Package Insert (for marketed products) or is not listed at the specificity or severity that has been observed. It is the responsibility of the IND sponsor to make this determination.

Serious and Unexpected Suspected Adverse Reaction (SUSAR): A SUSAR is an SAR that is both serious and unexpected.

Unanticipated Problem (UP): A UP is any event, incident, experience, or outcome that is

- 1. unexpected in terms of nature, severity, or frequency in relation to
  - a. the research risks that are described in the IRB-approved research protocol and informed consent document, Investigator's Brochure, or other study documents; and
  - b. the characteristics of the subject population being studied; and

- 2. possibly, probably, or definitely related to participation in the research; and
- 3. places subjects or others at a greater risk of harm (including physical, psychological, economic, or social harm) than was previously known or recognized. (Per the IND sponsor, an AE with a serious outcome will be considered increased risk.)

**Serious Unanticipated Problem (UP):** A UP that meets the definition of a Serious Adverse Event or compromises the safety, welfare or rights of subjects or others.

**Unanticipated Problem that is not an Adverse Event (UPnonAE):** A UP that does not fit the definition of an AE, but which may, in the opinion of the investigator, involve risk to the subject, affect others in the research study, or significantly impact the integrity of research data. Such events would be considered non-serious UPs. For example, we will report occurrences of breaches of confidentiality, accidental destruction of study records, or unaccounted-for study drug.

# 11.2 Documenting, Recording, and Reporting Adverse Events

AEs occurring from the time the informed consent is signed through study day 5 will be documented, recorded, and reported to the CSO.

The following signs or symptoms are induced by or associated with Methylprednisolone sodium succinate, and any combination of these is expected to occur. These events will not be recorded or reported to the CSO unless they reach a Grade of 3 or higher, are deemed a risk to the participants' rights or well-being, or are deemed appropriate to report under specific circumstances by the Principal Investigator:

- Hyperglycemia
- Leukocytosis
- Neutrophilia
- Monocytopenia
- Eosinopenia
- Flushing
- Increased appetite
- Bitter taste in mouth
- Metallic taste in mouth
- Anxiety

The following signs or symptoms are induced by or associated with Methylprednisolone sodium succinate. These events will not be recorded or reported to the CSO unless they reach a Grade of

4 or higher, are deemed a risk to the participants' rights or well-being, or are deemed appropriate to report under specific circumstances by the Principal Investigator:

• Lymphopenia (Lymphocyte Count Decreased)

The following signs or symptoms are induced by or associated with Methylprednisolone emulsion 1%, and any combination of these is expected to occur. These events will not be recorded or reported to the CSO, unless they reach a Grade of 3 or higher, are deemed a risk to the participants' rights or well-being, or are deemed appropriate to report under specific circumstances by the Principal Investigator:

- Application site burning
- Application site itching
- Application site redness

At each contact with the subject, information regarding AEs will be elicited by appropriate questioning and examinations and will be:

- immediately documented in the subject's medical record/source document,
- recorded in CRIMSON, and
- reported as outlined below (eg, IND sponsor, IRB, and Food and Drug Administration [FDA]).

If a diagnosis is clinically evident (or subsequently determined), the diagnosis rather than the individual signs and symptoms or lab abnormalities will be recorded as the AE.

All abnormal laboratory findings will be reviewed on a routine basis by the principal investigator to identify potential safety signals. An abnormal lab not included on the toxicity table should be assessed in a similar fashion to the criteria above.

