# 6.2 Infusion visit (Day 0)

- Targeted physical exam
- Vital signs on first encounter, every 30 minutes from the time of infusion until the time of collection of the four-hour blood sample, and discharge.
- Serum pregnancy test (for volunteers capable of becoming pregnant). For volunteers screened within the past 24 hours, the test will not be repeated.
- Interim medical history and medication review
- Pre-infusion blood draw (for analyses listed in Table 2)
- Optional: Pre-infusion skin biopsy from one arm
- Optional: Application of topical methylprednisolone to the contralateral arm
- Intravenous infusion of methylprednisolone sodium succinate (30 minutes)
- Nursing staff will monitor study subjects for the presence of behavioral abnormalities (altered mood, hyperactivity, disorientation, psychosis)
- Blood draws at 1 and 2 hours or 2 and 4 hours (+/-10 minutes) after the start of infusion (for analyses listed in Table 2)
- Optional: Skin biopsy (at the site where topical methylprednisolone was applied) 4 hours after the start of infusion

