# 6.3 Follow-up Phone Calls (Day 1 and Day 5)

Follow-up phone calls will be made one day (+/-0 days) and five days (+/-2 days) after discharge to document the presence or absence of side effects related to the skin biopsy or study drug.

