# 8 Potential Risks and Benefits

# 8.1 Risks

**Methylprednisolone sodium succinate infusion:** Side effects from a one-time, intravenous dose of methylprednisolone may include metallic or bitter taste in the mouth during and possibly after infusion, upset stomach, sleep disturbance (insomnia, sleepiness/fatigue), increased appetite, water retention, swelling in hands/ankles/feet, weight gain, temporary increase in blood glucose, temporary increase in blood pressure, mood disturbance or unusual behavior, electrolyte

imbalance, muscle cramps, back pain, headaches, and frequent urination lasting 1-2 weeks after infusion.

Individuals who received methylprednisolone to treat illness have had skin problems such as rash or dry skin, easy bruising, growth of body hair, irregular menstrual cycles, abnormal results of liver enzyme tests, enlargement of the liver, inflammation of the pancreas, numbness in the feet and hands, eye problems, and bone problems such as osteoporosis and damage to the hip bone. Many of these effects were dependent on the length of treatment and we do not expect that they will occur with a single dose.

Corticosteroids may decrease resistance to infection and the ability to localize infection. Infections with any pathogen in any location of the body may be associated with the use of corticosteroids alone or in combination with other immunosuppressive agents. Corticosteroids may reactivate or exacerbate latent fungal, bacterial, or viral infections. Individuals with known or suspected active or latent infections, as well as those using immunosuppressive agents, will be excluded from study participation. In addition, subjects will be advised to limit travel for 4 weeks following the methylprednisolone infusion.

Allergic reactions including anaphylactoid reaction, anaphylaxis and angioedema have been reported in patients receiving methylprednisolone.

Serious cardiac, musculoskeletal, neurologic/psychiatric and other side effects of intravenous methylprednisolone have been reported in patients with underlying disease. Such effects are not expected in this study involving administration of a single dose in healthy volunteers.

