There are reports of cardiac arrhythmias and/or cardiac arrest following the rapid administration of large IV doses of methylprednisolone (greater than 0.5 gram administered over a period of less than 10 minutes). Bradycardia has been reported during or after the administration of large doses of methylprednisolone sodium succinate, and may be unrelated to the speed or duration of infusion.

**Methylprednisolone emulsion:** The most common side effects are itching, burning and redness of skin. Allergic skin reactions are rare. The following side effects may occur: vesiculation folliculitis, hypertrichosis, skin thinning, telangiectasia, and perioral dermatitis. Systemic absorption of topically applied corticosteroids may occur, particularly under the following conditions: when large quantities are used, or when application is made to wide areas of the body, or to damaged skin, when potent topical corticosteroids are used, and when the occlusive dressing technique is applied. Depression of the hypothalamic-pituitary-adrenal axis with consequent suppression of the adrenal gland may occur. Benign increased intracranial pressure

has been rarely reported. Methylprednisolone emulsion must not be applied to the face or to skin crease areas, and should not come in contact with the eyes.

**Blood draw:** The risks of drawing blood include pain, bruising, bleeding, and, rarely, fainting or infection.

**Skin biopsy:** The risks of skin biopsy include local pain, bleeding, infection, and potential scar and keloid formation. The use of local and systemic glucocorticoids can increase the risk of infection and poor healing of the biopsy site. A local anesthetic administered prior to biopsy can cause a mild burning sensation upon injection, skin irritation and rarely allergic reaction. Oral analgesics will be used to manage pain.

**ECG:** An ECG is of minimal risk to the subjects and causes no significant side effects. Unexpected or incidental medical findings unrelated to the study may occur and may require the subject to follow up with an appropriate physician for standard medical care or follow up. The electrodes may feel cold when applied; in rare cases some people will develop a rash or skin irritations where the patches are placed. This type of irritation usually resolves by itself or occasionally with topical medication.

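### The last follow-up call may fall on day 3 or 4, before the adverse-event recording window closes on study day 5; a one-sided call window and one wording change would align them

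*Combined protocol and SAP*

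**What the plan says.** Section 11.2 opens with the recording rule: "AEs occurring from the time the informed consent is signed through study day 5 will be documented, recorded, and reported to the CSO". Later in the same section a second sentence carries no day limit: "At each contact with the subject, information regarding AEs will be elicited by appropriate questioning and examinations". It goes on to require that what is elicited be entered in the source record and the study database, and reported.

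Section 6.3 times the two follow-up calls at "one day (+/-0 days) and five days (+/-2 days) after discharge". It gives their purpose as finding out whether the drug or the biopsy has caused side effects. Section 3 gives the same purpose. It adds that a volunteer who mentions an event that might need treatment will be asked to come to the clinic. Section 6.2 labels the infusion visit Day 0, and Section 3 has volunteers discharged once the 2-hour or 4-hour samples are taken.

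On the risks, Section 8.1 says "Corticosteroids may decrease resistance to infection and the ability to localize infection" and, for the biopsy, "The use of local and systemic glucocorticoids can increase the risk of infection and poor healing of the biopsy site". Under Section 7 the wound is closed with foam or adhesive strips and dressed. The study schedule contains no later visit at which it would be inspected.

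**The concern.** The recording window and the last scheduled contact both sit at day 5 nominally, but only the call has a tolerance, and it runs in both directions. This has two consequences.

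First, an early call ends active enquiry before the window ends. An event starting after that call but by day 5 is one the protocol intends to record, yet nobody is scheduled to ask about it. A wound infection is an obvious example, since it may not show in the first days and is more likely to be learned of by asking than by waiting.

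Second, a late call can bring to light an event that began on day 6 or 7. The opening sentence of 11.2 places that event outside the window, while the sentence on contacts places it inside. Staff should not have to choose between the two.

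What is at stake is complete and consistent recording of non-serious events in healthy volunteers who stand to gain nothing directly from taking part.

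**Working it through.** **Inputs**

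- End of recording window: study day 5 (Section 11.2).
- Infusion: Day 0 (Section 6.2).
- Discharge: the same day, after the 2-hour or 4-hour samples (Section 3), so days after discharge equal study days.
- Second call: 5 days after discharge, tolerance 2 days either way (Section 6.3).

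**Call day under the current plan**

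Call day = discharge day + 5, plus or minus 2. Earliest: 0 + 5 - 2 = 3. Nominal: 0 + 5 = 5. Latest: 0 + 5 + 2 = 7. At the nominal timing the call and the window agree.

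**Mismatch by call day, in whole days**

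Window days left without scheduled enquiry = max(0, 5 - call day). Days covered by the call but beyond the opening rule = max(0, call day - 5).

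| Call day | Window days after the last call | Days asked about beyond day 5 |
|---|---|---|
| 3 | 5 - 3 = 2 | 0 |
| 4 | 5 - 4 = 1 | 0 |
| 5 | 0 | 0 |
| 6 | 0 | 6 - 5 = 1 |
| 7 | 0 | 7 - 5 = 2 |

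The two limits differ on four of the five permitted days, by one or two days. This counts permitted days. It does not say how often each would be used, because the protocol gives no distribution of call timing.

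**Early calls (day 3 or 4).** No later contact is scheduled, so the sentence on contacts cannot help. An event that a volunteer volunteers unprompted by day 5 is still inside the window and would be recorded. What is lost is the prompt.

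**Late calls (day 6 or 7).** Three places favour recording: the sentence on contacts in 11.2, and the stated purpose of the calls in Sections 3 and 6.3, none of which has a day-5 limit. Only the opening sentence of 11.2 points the other way. This is a conflict of wording, with the weight of the text on the side of recording.

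**After the change**

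With a tolerance of +2/-0, call day = 5 to 5 + 2 = 7, and max(0, 5 - call day) = 0 on each of those days. With the window ending at the later of day 5 and the call, it ends on day 5, 6 or 7 together with the call, so the third column is also 0 throughout.

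**The case against.** The strongest reply is that this is ordinary visit tolerance. Section 6.3 is headed Day 1 and Day 5, Section 11.2 ends at day 5, and a reasonable team would read them together. That is fair for late calls: the text already supports recording what is told on day 6 or 7, and it would be wrong to infer that such events are lost. It does not answer the early calls, where the tolerance lets the last enquiry come before the window closes.

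A second reply is that the volunteers are carefully screened: "Individuals with known or suspected active or latent infections, as well as those using immunosuppressive agents, will be excluded from study participation". This lowers the risk from infection already present. It does not address one acquired after the infusion or at the biopsy wound.

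Two stronger readings are tempting, and the documents do not support them.

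- **That follow-up is weeks too short.** A reader might infer this from the statement that "subjects will be advised to limit travel for 4 weeks following the methylprednisolone infusion". That advice is a precaution; the protocol does not call it a period of risk. Serious adverse events (Section 11.4.2) and unanticipated problems that are also adverse events (Section 11.4.3) have no end date for reporting. The consent pages and the Safety Review and Communications Plan were not available, and either may tell volunteers to report later problems. How long to enquire about non-serious events after a single dose is a judgement.
- **That a halt could be missed.** The halting rules in Section 11.6 are not tied to the 11.2 window. A known event of grade 3 or above counts whenever it began, and any safety issue can halt the study.

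**Conclusion.** The point holds as a minor improvement to safety capture. A permitted day-3 or day-4 call leaves the last two days, or last day, of the protocol's own recording window unsolicited. For day-6 and day-7 calls, 11.2 contains a wording conflict that other text largely resolves in favour of recording.

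The size is at most two days per volunteer in either direction. How many volunteers this would touch cannot be stated: the protocol gives neither the spread of call days nor a rate for events in those days. The wound-related part concerns only those who have the optional biopsies, whose number is not given. The primary genomic endpoint, the sample size and the analysis are unaffected, and a missed halt is unlikely.

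The conclusion assumes that discharge is on the day of infusion, as Section 3 describes, and that no document outside the supplied text narrows the call window.

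**What to change.** Make two edits.

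1. **Section 6.3:** set the second call at five days (+2/-0) after discharge, so that it can fall on day 5, 6 or 7 but never before the recording window ends.
2. **Section 11.2, opening sentence:** record adverse events from consent through study day 5 or the final follow-up call, whichever is later.

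Leave Section 11.4.2 as it is. Serious adverse event reporting has no end date now, and adding a period there could narrow it.

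The change adds no visit, call, procedure or blood draw, and the latest permitted call day stays at 7. A one-sided window is slightly harder to schedule, and a few more unrelated background events will be recorded. Because payment follows completion of participation (Section 10), a volunteer who would have been called on day 3 might be paid up to 5 - 3 = 2 days later. The amendment needs IRB approval under the Statement of Compliance, and the consent form should be checked for any statement of call timing.
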